7.5. Medical History

Patient medical, surgical, medication and treatment history will be reviewed from Study NS-065/NCNP-01-201 and reviewed throughout the study. The dates and descriptions of past events will be documented in source documents and captured in the relevant eCRF.

7.6. Weight and Height

Height and weight will be collected at the visits specified in Table 1. Standing height will be collected with the patient barefoot (without shoes). The participant's legs should be kept as close together as possible and the heels should be placed back as close to the wall as possible. Participant may hold on to an object to facilitate balance. If a participant is non-ambulant, the ulnar length will be used to calculate height. Ulnar length will be measured by the CE during functional assessments (see Section 7.14.7). Weight will be collected with the patient barefoot and wearing light-weight clothes. Height and weight should take approximately 2 minutes and are not associated with any risks. These measurements are routinely performed during standard clinical examinations of patients with DMD. Weight in kilograms (kg) and height in centimeters (cm) will be documented in source documents and captured in the relevant eCRF.

7.7. Vital Signs

Vital signs will be performed at each study visit as specified in Table 1. For each visit that includes a study drug administration, vital signs will be performed at pre-dose, at the end of infusion (+10 mins) (approximately 1 hour after initiation of infusion), and 2 hours (+/- 5 mins) after initiation of infusion. If a clinically significant change from pre-dose is observed at 2 hours after initiation

of infusion, the parameter is followed every 30 mins (+/- 5 mins) until return to no clinical significant change from pre-dose.

Vital signs will include the following:

- Systolic blood pressure
- Diastolic blood pressure
- Heart rate
- Temperature

Vital signs will be documented in source documents and captured in the relevant eCRF. Any clinically significant changes noted by the investigator should be reported as an adverse event and should be addressed as clinically appropriate.

The site PI and the home infusion nurse will discuss vital sign parameters for each participant individually who is eligible and has elected to receive home infusions. To develop these guidelines, the site PI will take into consideration the range of clinically safe vital signs that have been observed from the participant during past study site infusions. The home infusion nurse will consult with the site investigator for any confirmed vital signs outside of these parameters (low or high).

7.8. Physical and Neurological Examination

The physical examination will be performed at the visits specified in Table 1 to assess any changes in physical presentation and symptoms. Physical examinations will include an assessment of the following:

- General appearance
- HEENT (head, ears, eyes, nose, and throat)
- Skin
- Lymph nodes
- Heart, including rhythm, heart sounds and presence of cardiac abnormalities
- Lungs
- Abdomen
- Extremities/joints
- Nervous system

- Any additional assessments necessary to establish baseline status or evaluate symptoms or adverse experiences

Documentation of the physical examination findings will be included in the source documentation at the clinical site. Only changes from baseline physical examination findings that meet the definition of an adverse event will be recorded on the adverse event page of the eCRF.

7.9. Renal and Urinary Bladder Ultrasound

Renal ultrasound will include imaging of the kidneys, ureters, and bladder and be performed at visits specified in the schedule of study assessments. Ultrasound of the kidneys, ureters and bladder will be assessed by local urologists or other trained medical professionals.

7.10. Adverse Events and Serious Adverse Events

Investigators will assess the occurrence of AEs and SAEs each study visit or patient contact during the study. AEs and SAEs may be reported by the patient/parent, discovered upon questioning, detected during examinations or review of test and lab results. AEs and SAEs should be documented in the source documents and the relevant eCRF with a full description including the nature, date and time of onset and resolution, determination of seriousness, severity, causality, corrective treatment, and outcome. Refer to Section 9 for safety procedures and reporting.

7.11. 12-Lead Electrocardiograms

A standard 12 lead ECG will be performed at the visits specified in the Schedule of Study Assessments (Table 1). ECG collection will be preceded by a 10-minute rest time during which the patient will remain in the supine position. At all time-points, ECGs will be collected prior to blood collection. ECG results will be based on machine readings and interpretation by local cardiologist or other trained medical professionals. ECG results will be recorded in the eCRF.

7.12. Clinical Laboratory Tests

Clinical laboratory assessments will be performed at visits specified in the Schedule of Assessments table (Table 1). Any blood sampling that occurs during the IP infusion should be collected from a location away from the IP infusion placement (i.e. opposite arm).

7.12.1. Sample Collection, Storage, and Shipping

Each patient will have blood drawn and urine collected for the blood and urine laboratory safety assessments as listed/described in the sections below, including hematology, chemistry, BNP, urinalysis, urine cytology, cytokines, anti-dystrophin antibody, and anti-NS-065/NCNP-01 antibody.

Laboratory safety assessments will be performed at the visits specified in Table 1. Samples will be collected by a trained member of the study team. This assessment is associated with the usual risks of a blood draw which include pain, bruise at the point where the blood is taken, redness and swelling of the vein, infection, and a rare risk of fainting. In order to decrease any of these possible risks the sites will employ pediatric trained staff and will use a numbing cream, if desired by the patient, to reduce the risk of pain.

All blood and urine samples will be sent to the designated central laboratory for testing unless otherwise noted. The procedures for the collection, handling, and shipping of laboratory samples will be specified in the Laboratory manual. Clinical laboratory tests are listed in **Error! Reference source not found.**

Table 2. Clinical Laboratory Tests**Hematology, Chemistry, Urinalysis and Urine Cytology – Safety Labs**

- **Hematology**
 - o Red blood cell count
 - o Hemoglobin
 - o Hematocrit
 - o Reticulocyte count
 - o Mean corpuscular volume
 - o Mean corpuscular hemoglobin
 - o Mean corpuscular hemoglobin concentration
 - o White blood cell count
 - o White blood cell differential
 - o Platelet count
 - o Fibrinogen
 - o Activated partial thromboplastin time
 - o Prothrombin international normalization ratio
- **Blood Chemistry**
 - o Sodium
 - o Potassium
 - o Chloride
 - o Calcium
 - o Inorganic Phosphorus
 - o Blood Urea Nitrogen
 - o Creatinine
 - o Cystatin C
 - o Aspartate aminotransferase
 - o Alanine aminotransferase
 - o Gamma-glutamyl transferase
 - o Alkaline phosphatase
 - o Haptoglobin
 - o Lactate dehydrogenase
 - o Creatine kinase
 - o Total bilirubin (Direct/Indirect)
 - o Total protein
 - o Albumin
 - o Albumin to globulin ratio
 - o Total cholesterol
 - o Triglyceride
 - o Blood glucose
 - o C-reactive protein
- **Brain Natriuretic Protein (BNP)**
 - **Urinalysis**
 - Urinalysis includes:
 - o Urine glucose
 - o Urine blood
 - o Urine urobilinogen
 - o Urine specific gravity
 - o Urine osmolality
 - o Urinary sediment (erythrocytes, WBC, Casts, epithelium, crystals)
 - o Urine protein (benzethonium chloride method)
 - o Urine protein (benzethonium chloride method)
 - o Urine microalbumin
 - o Urine N-acetyl-beta-D-glucosaminidase
 - o Urine α 1-microglobulin
 - o Urine Creatinine
 - o Urine Cytology

7.12.2. Cytokine Testing

Cytokine testing will be performed at visits as specified in the Schedule of Assessments (Table 1). The following tests will be performed: IL-6, TNF- α , MCP-1. Blood will be drawn from patients at pre-dose and 9 hours (+/- 30min) after initiation of infusion at Weeks 37, 49, 73, 97, and the early termination.

7.12.3. Anti-Dystrophin Antibody

Anti-dystrophin antibody testing will be performed on serum samples collected predose during the visits specified in the Schedule of Assessments (Table 1). Samples will be analyzed by Shin Nippon Biomedical Laboratories, Ltd. (Japan).

7.12.4. Anti-NS-065/NCNP-01 Antibody

Anti-NS-065/NCNP-01 antibody testing will be performed on serum samples collected pre-dose during the visits specified in the Schedule of Assessments (Table 1). Samples will be analyzed by Shin Nippon Biomedical Laboratories, Ltd. (Japan).

7.13. Pharmacodynamics and Efficacy Assessments

7.13.1. Serum Pharmacodynamic Biomarkers

Serum samples will be collected and stored for future pharmacodynamic biomarker studies.

7.14. Function and Strength

All function and strength testing will be performed by a trained clinical evaluator (CE). Assistive devices may be utilized during the testing as specified in the study Manual of Operations. The same CE should perform testing on the same patient throughout the study when possible.

7.14.1. Time to Stand (TTSTAND) - Primary Efficacy Endpoint

TTSTAND will be performed by a CE at visits specified in the schedule of study assessments (Table 1). This test will assess the time it takes the patient to go from lying flat on the floor to standing and is administered as part of the NSAA (see Section 7.14.4). This test should take approximately 1 minute and is not associated with any risks. This test is routinely performed during standard clinical examinations of patients with DMD. The number of seconds required to perform the test and the 6-point rating scale of how the patient attains the standing position will be documented in source documents and captured in the relevant eCRF.

7.14.2. Time to Run/Walk 10 Meters (TTRW)

TTRW will be performed by a CE at visits specified in the schedule of study assessments (Table 1). This test will assess the time it takes the patient to walk/run 10 meters including a 6-point rating scale for quality of the run/walk administered as part of the NSAA (see Section 7.14.4). This assessment should take 2 minutes and can be associated with falls; however, these are infrequently

reported. The number of seconds required to perform the test will be documented in source documents and captured in the relevant eCRF.

7.14.3. Time to climb 4 stairs (TTCLIMB)

TTCLIMB will be performed by a CE at visits specified in the schedule of study assessments (Table 1). This test will assess the time it takes the patient to climb 4 stairs (23) including a 6-point rating scale to assess how the patient negotiates the stairs administered as part of the NSAA (see Section 7.14.4). This test should take approximately 1 minute and is not associated with any risks. The number of seconds required to perform the test will be documented in source documents and captured in the relevant eCRF.

7.14.4. North Star Ambulatory Assessment (NSAA)

NSAA will be performed by a CE at visits specified in the schedule of study assessments (Table 1). The NSAA is a clinician rated, 17-item, functional scale originally designed for ambulant boys with DMD who are able to ambulate at least 10 meters (24). This evaluation tool assesses functional activities including standing, getting up from the floor, negotiating steps, hopping, and running. The assessment is based on a 3-point rating scale of 2 = ability to perform the test normally, 1 = modified method or assistance to perform test, 0 = unable to perform the test. Thus, total score can range from 0 (completely non-ambulant) to 34 no impairment on these assessments. Individual test item scores and total score will be recorded in source documents and in the relevant eCRF. This test should take approximately 10 minutes and is not associated with any risks. The NSAA should be administered before the 6MWT at each occurrence.

7.14.5. Six-minute Walk Test (6MWT)

6MWT will be performed by a CE at visits specified in the schedule of study assessments (Table 1). The 6MWT is a widely used and accepted test in numerous diseases. The version of the 6MWT adapted for use in DMD will be used (25). To perform the test, two points (cones) are set 25 meters apart and patients are asked to walk back and forth, between the cones quickly and safely for 6 minutes. The total distance in meters that the patient walks in 6 minutes is recorded. This test is considered a simple, standardized, low-technology and cost-effective means of clinically assessing 1) functional motor status and 2) integrated and global responses to exercise. The CE will measure the number of steps taken by the patient for the first 50 meters and total meters walked in 6 minutes. This test should take approximately 10 minutes. The 6MWT may cause feelings of

pressure or pain in the patient's chest, difficulty breathing, and shortness of breath. The 6MWT may also cause an increased risk of falling and muscle cramping.

7.14.6. Quantitative Muscle Testing (QMT)

QMT will be performed by a CE at visits specified in the schedule of study assessments (Table 1). QMT assessments are designed to measure muscle force production during an isometric contraction. QMT is a well-established method for measuring muscle weakness in neuromuscular disease (26). Patients will be placed on an examination table with a back-support system to eliminate the need for manual back stabilization. Following a single practice administration, each patient will complete a scored QMT evaluation (perform 2 tests; with the higher of the 2 values used for data analysis). QMT will be performed by recording force in pounds through a direct computer interface with a strain gauge. Testing positions and test order will be standardized. Bilateral testing of the muscle groups listed below will be performed:

- Handgrip
- Elbow flexors (biceps)
- Elbow extensors (triceps)
- Knee flexors (hamstrings)
- Knee extensors (quadriceps)

7.14.7. Ulnar Length

Ulnar length will be measured by a CE at visits specified in the schedule of study assessments (Table 1). In the event that a patient becomes non-ambulant the ulnar length will be utilized to impute height.

7.15. Pharmacokinetic Assessments

7.15.1. Collection and Assessment of Pharmacokinetic Samples

Blood samples for pharmacokinetic (PK) assessments will be taken at visits specified in the study assessment table (Table 1). PK sampling times are measured from the start of infusion. Infusion is expected to take approximately 1 hour to complete. PK samples will be analyzed in the event that anti-NS-065/NCNP-01 antibodies are detected in order to understand the impact of

immunogenicity on plasma levels of the drug. Blood will be drawn from patients at pre-dose, 2 hours (+/- 5 min) and 9 hours (+/- 5 min) after initiation of infusion at Weeks 37, 49, 73, and 97.

7.15.2. Shipment of Pharmacokinetic Samples

Plasma PK samples will be shipped frozen on dry ice according to instructions provided in the Laboratory Manual.

7.16. Total Blood Volume of Clinical Laboratory and Pharmacokinetic Samples

The total number of venipunctures and total volume of whole blood collected during the study will be limited to that needed for safety monitoring and efficacy assessments. Total scheduled whole blood volume collected over the study duration is not to exceed 321.1 mL for each patient. In the event of an SAE or an AE, additional blood may be taken for safety assessments based on timing and clinical judgement from PI, study chair and medical monitor. A breakdown of total volume of blood collected is summarized in **Error! Reference source not found.**

Table 3. Blood Sample Number and Volume

Tests	WK 25 ^c	WK 29	WK 33	WK 37	WK 41	WK 45	WK 49	WK 61	WK 73	WK 85	WK 97	WK 109	WK 121	WK 133	WK 145	WK 157	WK 169	WK 181	WK 193	WK 205	WK 217 or ET	Total mL of Blood	
Safety	10.6	10.6	10.6	10.6	10.6	10.6	10.6	10.6	10.6	10.6	10.6	10.6	10.6	10.6	10.6	10.6	10.6	10.6	10.6	10.6	10.6	222.6	
BNP	3.0						3.0		3.0		3.0		3.0		3.0		3.0		3.0		3.0		27.0
PD				1.0			1.0		1.0		1.0		1.0		1.0		1.0		1.0		1.0		9.0
PK ^{a,b}				6.0			6.0		6.0		6.0												24.0
Cytokine				4.0			4.0		4.0		4.0												16.0
Anti-dystrophin & Anti-NS-065/NCNP-01				2.5			2.5		2.5		2.5		2.5		2.5		2.5		2.5		2.5		22.5
Approximately total volume of blood per patient^e																						321.1	

a. Blood samples for PK analysis are collected according to the schedule in Section 7.15

b. For SAEs, additional blood draws for PK and immunogenicity will be based on timing and clinical judgement from PI, study chair and medical monitor.

c. Blood samples for safety analysis at Week 25 will be collected at the Week 25 of Study NS-065/NCNP-01-201.

d. Early termination (ET) blood draw volumes based on clinical judgement from PI, study chair and medical monitor.

e. Total volume of blood per patient does not include any additional testing that may be required for follow-up of AEs or re-testing and follow-up of abnormal laboratory results.

Total volume based on maximum expected blood draw from Week 25 through Week 217.

8. STUDY ACTIVITIES

8.1. Treatment Phase

In anticipation of the Week 50 study visit, which is the first study visit where optional home infusion could take place, the option of home infusion can be introduced to the patient by the study physician. Home infusion, which is limited to selected visits described below, is not required for participation in this study. The option of home infusion should be considered if the study physician believes that it will help the patient to derive safety, benefit and convenience from participation in the trial. The routine study visits that are eligible to be conducted in the home are limited to those whose study procedures do not extend beyond the following list: investigational product administration, vital signs collection, review of medical, surgical, medication and treatment history, and AE review. Specifically, visits 53, 57, 61, 65, 69, 73, 77, 81, 85, 89, 93, 97, 101, 105, 109, 113, 117, 121, 125, 129, 133, 137, 141, 145, 149, 153, 157, 161, 165, 169, 173, 177, 181, 185, 189, 193, 197, 201, 205, 209, 213 and 217 (or early termination) must be conducted at the study site and are not eligible for home infusion. Participation in optional home infusion requires written approval from the study sponsor, study chair, medical monitor and site PI. As advised by the study chair, medical monitor, and site PI, infusions taking place outside of the primary study site (e.g. home infusion) would only be considered starting at the Week 50 study visit or after, if the participant had not experienced any significant adverse events related to infusion of the investigational product. Patients must also reside in a municipality or region with access to emergency medical services (such as 911) to participate in home infusions. The study sponsor approval will only occur following endorsement by the Nippon Shinyaku Chief Medical Officer. The safety monitoring by the site PI, sponsor, study chair and medical monitor will continue throughout the treatment phase for all study visits, without regard for whether the infusion occurs at the study site or the home. Furthermore, the site PI is responsible for immediate contact with the study chair and medical monitor for any safety concern, without regard for whether the infusion occurs at the study site or the home.

All visit activities are to occur in the order in which they are listed below.

8.1.1. Day of First Infusion (Week 25)

The Week 25 study visit of Study NS-065/NCNP-01-201 shall also serve as the Week 25 dose visit if the patient wishes to continue into Extension Study NS-065/NCNP-01-202. In order to accommodate patient recovery following the scheduled biopsy during the Week 25 of Study NS-065/NCNP-01-201, patients will be allowed a visit window of 7 days (+/- 3 days) from the Week 24 infusion to complete both the end of study procedures and the first infusion in the extension study. All Week 25 study assessments of the NS-065/NCNP-01-201 study, including muscle biopsy, must be completed prior to first infusion in this extension study. Patients can receive the first infusion of this extension study on the same day as the Week 25 study visit of NS-065/NCNP-01-201, as long as all study assessments (including muscle biopsy) of NS-065/NCNP-01-201 are completed prior to infusion. Initial and Week 25 study assessments of NS-065/NCNP-01-201 will be used as baseline values for this extension study.

At Week 25 of Extension Study NS-065/NCNP-01-202, the following activities will occur:

- Inclusion/Exclusion Confirmation and Review
- Review of Medical, Surgical, Medication, and Treatment History (confirmation of concomitant medications and other treatments; any changes will be noted)*
- AE Review*
- Vital signs
- Blood draw for BNP (note this assessment may be collected with the other laboratory assessment draws for week 25 as part of Study NS-065/NCNP-01-201)
- Investigational product administration

*If Week 25 of the Extension Study occurs on the same day as Week 25 of NS-065/NCNP-01-201, these assessments do not need to be repeated.

8.1.2. Routine Infusion Visits

These visits will occur at: Weeks 26-28, 30-32, 34-36, 38-40, 42-44, 46-48, 50-52, 54-56, 58-60, 62-64, 66-68, 70-72, 74-76, 78-80, 82-84, 86-88, 90-92, 94-96, 98-100, 102-104, 106-108, 110-112, 114-116, 118-120, 122-124, 126-128, 130-132, 134-136, 138-140, 142-144, 146-148, 150-152, 154-156, 158-160, 162-164, 166-168, 170-172, 174-176, 178-180, 182-184, 186-188, 190-192, 194-196, 198-200, 202-204, 206-208, 210-212 and 214-216.

At these visits the following activities will occur:

- Review of Medical, Surgical, Medication and Treatment History
- AE Review
- Vital Signs
- Investigational product administration

8.1.3. Weeks 29, 33, 41, and 45

At these visits the following activities will occur:

- Review of Medical, Surgical, Medication, and Treatment History
- AE Review
- Weight
- Vital Signs
- Physical and Neurological Exam
- Hematology
- Chemistry
- Urinalysis (Random Urine)
- Investigational product administration

8.1.4. Week 37, 49, 73, and 97

At the visit the following activities will occur:

- Review of Medical, Surgical, Medication, and Treatment History
- AE Review
- Height & Weight
- Vital Signs
- Physical and Neurological Exam
- 12-Lead ECG
- Function and Strength:
 - TTSTAND
 - TTRW
 - TTCLIMB

- NSAA
- 6MWT
- QMT
- Ulnar Length
- Hematology
- Chemistry
- Blood draw for BNP (at Week 49, 73, and 97)
- Urinalysis (Random Urine)
- Cytokine
- Anti-dystrophin antibody (pre-dose)
- Anti-NS-065/NCNP-01 antibody (pre-dose)
- Serum PD biomarker
- Investigational product administration
- PK Blood

8.1.5. Routine Infusion Visits with Weight Collection

These visits occur at: Weeks 53, 57, 65, 69, 77, 81, 89, 93, 101, 105, 113, 117, 125, 129, 137, 141, 149, 153, 161, 165, 173, 177, 185, 189, 197, 201, 209, and 213. At these visits the following activities will occur:

- Review of Medical, Surgical, Medication, and Treatment History
- AE Review
- Weight
- Vital Signs
- Investigational product administration

8.1.6. Weeks 61, 85, 109, 133, 157, 181, and 205

At these visits the following activities will occur:

- Review of Medical, Surgical, Medication, and Treatment History
- AE Review
- Height & Weight,

- Vital Signs
- Physical and Neurological Exam
- Function and Strength:
 - TTSTAND
 - TTRW
 - TTCLIMB
 - NSAA
 - 6MWT
 - QMT
 - Ulnar Length
- Hematology
- Chemistry
- Urinalysis (predose and first void taken within 5 hours postdose)
- Urine Cytology (pre-dose) (133, 157 and 181 only)
- Renal and Urinary Bladder Ultrasound (Visits 133, 157 and 181 only)
- Investigational product administration

8.1.7. Week 121, 145, 169, and 193

At the visit the following activities will occur:

- Review of Medical, Surgical, Medication, and Treatment History
- AE Review
- Height & Weight
- Vital Signs
- Physical and Neurological Exam
- 12-Lead ECG
- Function and Strength:
 - TTSTAND
 - TTRW
 - TTCLIMB
 - NSAA

- 6MWT
- QMT
- Ulnar Length
- Hematology
- Chemistry
- Blood draw for BNP
- Urinalysis (predose and first void taken within 5 hours postdose)
- Urine Cytology (pre-dose) (Visits 145 and 169 only)
- Renal and Urinary Bladder Ultrasound (Visits 145 and 169 only)
- Anti-dystrophin antibody (pre-dose)
- Anti-NS-065/NCNP-01 antibody (pre-dose)
- Serum PD biomarker
- Investigational product administration

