Moreover, no anti-NS-065/NCNP-01 antibodies were detected in the 13-week or 26-week mouse studies or in the 39-week monkey study. Anti-NS-065/NCNP-01 antibodies were detected in one monkey at 200mg/kg in the 12-week monkey study. However, antibody detection was not considered to affect the toxicological evaluation in this study, since skipping efficiency was confirmed in the muscle of this animal at the end of the treatment period and no remarkable decrease in exposure to NS-065/NCNP-01 was observed after repeated dosing. Based on these data, the NOAELs were concluded to be 60 and 15 mg/kg/dose in 13-week and 26-week mouse studies respectively and 60 mg/kg/dose in 12-week and 39-week monkey studies respectively. Both the in vitro and in vivo genotoxicity studies were negative.

NS-065/NCNP-01 was administered once weekly for 26 weeks at a dose level of 0 (vehicle: physiological saline), 50, 150 and 500 mg/kg (51 mice per group) male CByB6F1-Tg(HRAS)2Jic mice via intravenous route with a bolus injection. After the terminal necropsy, macroscopic examinations showed a mass and/or thickening in one side of the ureter in one mouse at 50 mg/kg, in two mice at 150 mg/kg, and no findings at 500 mg/kg dose group. In subsequent histopathological examinations on these three mice, transitional cell carcinoma was noted. Histopathological examination of the ureters for the other mice was conducted and no further tumorigenic changes were identified. Additionally, no treatment-related tumors were noted in any other organs. The blood concentration of NS-065/NCNP-01 in mice who received 50 mg/kg/wk was lower than the blood concentration of NS-065/NCNP-01 expected in human patients who will receive 80mg/kg/wk.

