Pharmacokinetics and Pharmacodynamics	Pharmacokinetics and Pharmacodynamics													
PK (Blood) ¹¹														
Serum PD Biomarker												X		

Notes:

1. Week 25 of Study NS-065/NCNP-01-201 will also serve as Week 25 for first dose of Study NS-065/NCNP-01-202. End of study procedures of Study NS-065/NCNP-01-201 must be completed prior to dosing in Extension Study NS-065/NCNP-01-202
2. Perform vitals at pre-dose, at the end of infusion (+10 mins) and 1 hr (+/- 5 mins)
3. Hematology: RBC, Hb, Ht, Ret, MCV, MCH, MCHC, WBC, PLT, WBC Differential Fibrinogen, aPTT, PT-INR
4. Chemistry: Na, K, Cl, Ca, IP, BUN, Serum Creatinine, Cystatin C, AST, ALT, GGT, ALP, Haptoglobin, LDH/LDH isozyme, CK, Total bilirubin (Direct/Indirect), Total protein, Albumin, Albumin to globulin ratio, Total cholesterol, Triglyceride, Blood glucose, C-reactive protein
5. Urinalysis (Random Urine): Urine glucose, Urine blood, Urine urobilinogen, Urine specific gravity, Urine osmolarity, Urinary sediment (RBC, WBC, Cast), Urine protein (benzethonium chloride method), Albumin in urine, NAG in urine, α 1-microglobulin in urine, Urine Creatinine
6. Urine Cytology is collected along with pre-dose Urinalysis. Following Protocol Amendment 9.0 approval, the assessment should be performed at the next clinic visit, then every 6 months thereafter (i.e. Visits 133, 157, 181 and 193 or Visits 145, 169, 193, 205 and 217). Urine Cytology is collected at Visit 217 for all subjects.
7. 24hr pooled Urine in Study NS-065/NCNP-01-201 only: Urine protein (benzethonium chloride method) , Albumin in urine, NAG in urine, α 1-microglobulin in urine, Urine Cr, Urine Na, Urine K, Urine Cl, Urine IP, Uric acid in urine, β 2-microglobulin in urine and PK
8. Renal Ultrasound includes imaging of kidneys, bladder and ureters. Following Protocol Amendment 9.0 approval, the assessment should be performed at the next clinic visit, then every 6 months thereafter (i.e. Visits 133, 157, 181 and 193 or Visits 145, 169, 193, 205 and 217). Renal Ultrasound is collected at Visit 217 for all subjects.
9. Cytokine: IL-6, TNF- α , MCP-1 at pre-dose and 8hr (\pm 30min) after end of infusion
10. Function and Strength: Time to Stand (TTSTAND), Time to Climb (TTCLIMB), Time to run/walk 10 meters (TTRW), Six-minute walk Test (6MWT), North Start Ambulatory Assessment (NSAA), Quantitative Muscle Testing (QMT) and Ulnar Length
11. PK sampling timepoints: pre-dose, 1hr (+/- 5 mins) and 8hr (+/- 5 mins) after the end of the infusion

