8.2. Post-Treatment Phase

8.2.1. Week 217 or Early Termination Visit

The following activities will occur at the end of the treatment (Week 217) for all patients. If a patient withdraws from the study or is withdrawn by the site PI (Early Termination Visit) the activities listed below should be completed. All visit activities are to occur in the order in which they are listed below.

- Review of Medical, Surgical, Medication, and Treatment History
- AE Review
- Height & Weight
- Vital Signs
- Physical and Neurological Exam
- 12-Lead ECG
- Function and Strength:
 - TTSTAND
 - TTRW

- TTCLIMB
- NSAA
- 6MWT
- QMT
- Ulnar Length
- Hematology
- Chemistry
- Blood draw for BNP
- Urinalysis (Random Urine)
- Urine Cytology
- Renal and Urinary Bladder Ultrasound
- Serum PD biomarker

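### Section 8 excludes urine cytology and renal/bladder ultrasound at Visits 193 and 205, where Table 1 requires them, leaving at least 36 weeks without either test

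*Combined protocol and SAP*

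**What the plan says.** Table 1, notes 6 (cytology) and 8 (ultrasound), gives the same rule for both tests: a first assessment at the next clinic visit after approval of Amendment 9, "then every 6 months thereafter (i.e. Visits 133, 157, 181 and 193 or Visits 145, 169, 193, 205 and 217". Both notes add Visit 217 for every patient. The Table 1 grid also marks both tests at Week 193 and in the last column of that page, which appears to be Week 205.

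Section 8 lists activities visit by visit:

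- Section 8.1.6 is headed for Weeks 61, 85, 109, 133, 157, 181 and 205. It has "Renal and Urinary Bladder Ultrasound (Visits 133, 157 and 181 only" and the same limit for cytology.
- Section 8.1.7 is headed for Weeks 121, 145, 169 and 193. It has "Urine Cytology (pre-dose) (Visits 145 and 169 only" and the same limit for ultrasound.
- Section 8.2.1 includes both tests at the final or early-termination visit: "The following activities will occur at the end of the treatment (Week 217) for all patients".

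On which text sets the timing, Section 7.9 says ultrasound will "be performed at visits specified in the schedule of study assessments". Section 7.12.1, whose list of laboratory assessments includes urine cytology, says "Laboratory safety assessments will be performed at the visits specified in Table 1". Section 8.1 says of its own lists: "All visit activities are to occur in the order in which they are listed below".

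**The concern.** Weeks 193 and 205 are in the headings of Sections 8.1.7 and 8.1.6, so the word *only* excludes those visits. It is not mere silence. A site that tests at Week 193 departs from Section 8, and a site that does not test departs from Table 1.

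The two tests answer a specific signal. Section 1.3.4 reports ureteral masses or thickening in one mouse at 50 mg/kg and two at 150 mg/kg: "In subsequent histopathological examinations on these three mice, transitional cell carcinoma was noted". The same section reports no such finding at 500 mg/kg and no treatment-related tumours in other organs. It also says that blood concentration at 50 mg/kg was below that expected in patients on 80 mg/kg/week. Appendix 3 (Amendment 9) confirms that both tests were added because of new pre-clinical findings.

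The excluded visits fall late in treatment. Under Amendment 10 the boys on 40 mg/kg/week move to 80 mg/kg/week, and treatment is extended to Week 216. Safety is a primary objective in about 16 patients at up to 6 sites. If sites follow different sections, interim cytology and imaging will be uneven in an already small dataset.

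**Working it through.** The check is the difference in weeks between consecutive test visits, compared with the six-month rule.

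**Inputs.** Visit weeks come from Table 1 notes 6 and 8 and from Sections 8.1.6, 8.1.7 and 8.2.1. Conversion: months = weeks × 7 / 30.44. Six months is therefore 6 × 30.44 / 7 = 26.1 weeks.

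**The plan's own rule.** The notes' two tracks, with Visit 217 for everyone, keep within six months. Their longest gap is 24 weeks, and 24 × 7 / 30.44 = 5.5 months.

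| Reading | Visits | Gaps (weeks) | Longest |
|---|---|---|---|
| Notes, 133 track | 133, 157, 181, 193, 217 | 24, 24, 12, 24 | 24 (5.5 months) |
| Notes, 145 track | 145, 169, 193, 205, 217 | 24, 24, 12, 12 | 24 (5.5 months) |
| Section 8 alone | 133, 145, 157, 169, 181, 217 | 12, 12, 12, 12, 36 | 36 (8.3 months) |
| 133 track within Section 8's limits | 133, 157, 181, 217 | 24, 24, 36 | 36 (8.3 months) |
| 145 track within Section 8's limits | 145, 169, 217 | 24, 48 | 48 (11.0 months) |

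The last three rows all exceed 26.1 weeks. The 36-week gap is 36 / 192 = 19% of the extension's planned treatment weeks.

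**With Visit 193 restored to Section 8.1.7**

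- Section 8 alone: 12, 12, 12, 12, 12, 24
- 133 track: 24, 24, 12, 24
- 145 track: 24, 24, 24

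The longest gap is then 24 weeks in every reading. Restoring Visit 205 on the 145 track as well gives 24, 24, 12, 12, which is exactly what the notes list. Visit 193 is therefore the addition that brings the interval back within six months. Visit 205 removes the remaining disagreement with the notes.

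**The case against.** The strongest reply is that a careful site would follow Table 1. Section 7.1 presents Table 1 as the schedule, Sections 7.9 and 7.12.1 send timing there, and no section sends timing to Section 8. The sentence in Section 8.1 about order concerns sequence within a visit, not which visits carry a test. Section 8 is also incomplete elsewhere: its Week 217 list omits the antibody tests that Table 1 and the synopsis place there. All of this is correct and makes Table 1 the better reading. It does not remove the conflict. No clause gives Table 1 precedence, and Section 8 excludes the tests in express terms.

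The 48-week figure can be called artificial, because the 145 track exists only in the notes, and the phrase that defines it also names Visits 193, 205 and 217. That is fair. The figure describes a site that combines the two texts, and the 36-week figure does not need it.

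The notes also contain 12-week steps, so they are not strictly six-monthly, and Visit 205 might fit better on the 133 track. This stands as an observation. It does not breach the rule, since neither track exceeds 24 weeks.

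The consequence is also limited. Both tests are done at Week 217 or early termination, urinalysis continues at Weeks 193 and 205, and Section 9.5.3 makes confirmed haematuria an event of special interest. Section 10.5.1 names neither test among its summaries. The effect is on monitoring and on the completeness of safety data, not on an efficacy result.

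**Conclusion.** The concern holds. Sections 8.1.6 and 8.1.7 contradict Table 1 notes 6 and 8 in current text. Followed as written, Section 8 leaves 36 weeks without cytology or ultrasound, or 48 weeks for a 145-track patient held to its limits, against a maximum of 24 weeks under the notes. These figures assume that the patient starts at Visit 133 or 145, continues to Week 217, and attends at nominal weeks. An early-termination visit would shorten the last gap. A site that follows Table 1 has no gap over 24 weeks.

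This is an operative safety instruction that is wrong as written and should be corrected. What is at risk is interim tumour-directed testing late in treatment, not urinary monitoring as a whole.

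**What to change.** In Section 8.1.7, change the cytology and ultrasound lines to Visits 145, 169 and 193. In Section 8.1.6, add Visit 205 to both lines for patients on the 145 track. Alternatively, replace all four limits with a reference to Table 1 notes 6 and 8, so that the schedule is stated in one place. The notes can stay as they are.

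The cost is four lines in a clarification memo or small amendment. No test is added beyond those Table 1 already requires.
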